STUDY PROTOCOL SUMMARY

TITLE

Descriptive: Role of endomyocardial biopsy and aetiology-based treatment in patients with inflammatory heart disease in arrhythmic and non-arrhythmic clinical presentations: an integrated approach for the optimal diagnostic and therapeutic management.

Code: MYOCAR

Final protocol date: 20/02/2020 (V03 - Multicenter)

HEAD CENTER

Department of Electrophysiology and Arrhythmology, San Raffaele Hospital, Milan, Italy.

INVESTIGATORS

Principal Investigators: [name] – [name]

Promoter: [name] [name], Head Department of Electrophysiology and Arrhythmology, San Raffaele Hospital, Milan, Italy

BACKGROUND

Myocarditis is a complex inflammatory disease, usually occurring secondary to viral infections, autoimmune processes or toxic agents [1]. Clinical presentations are multiple, including chest-pain, heart failure and a broad spectrum of arrhythmias [1]. In turn, outcome is largely unpredictable, ranging from mild self-limiting disease, to chronic stage and progressive evolution towards dilated cardiomyopathy, to rapid adverse outcome in fulminant forms [1,2]. Subsequently, myocarditis is often underdiagnosed and undertreated [3], and optimal diagnostic and therapeutic strategies are still to be defined.

RATIONALE

Our study aims at answering multiple questions about myocarditis, with special attention

to its arrhythmic manifestations.

- 1. Optimal diagnostic workflow is still to be defined. In fact, although endomyocardial biopsy (EMB) is still the diagnostic gold standard, especially for aetiology identification [1], it is an invasive technique. Furthermore, it may lack sensitivity because of sampling errors. By converse, modern imaging techniques cardiac magnetic resonance (CMR) in particular have been proposed as alternative or complementary diagnostic tool in inflammatory heart disease [4,5,6]. Other noninvasive diagnostic techniques, like delayed-enhanced CT (DECT) scan or position emission tomography (PET) scan, are under investigation.
- 2. Biomarkers to identify myocarditis aetiology, predisposition, prognosis and response to treatment are still to be defined [1,3,5].
- 3. Arrhythmic myocarditis is largely underdiagnosed and uninvestigated. Importantly, myocarditis presenting with arrhythmias requires specific diagnostic, prognostic and therapeutic considerations [2]. At our hospital, which is an international referral center for ventricular arrhythmias management and ablation, a relevant number of patients with unexplained arrhythmias had myocarditis as underlying aetiology. Our experience may considerably improve knowledge and management of arrhythmic myocarditis.
- 4. The role of CMR, as well as alternative nonivasive imaging techniques, in defining myocarditis healing is a relevant issue. In particular, optimal timing for follow-up diagnostic reassessment is still to be defined, in patients with myocarditis at different inflammatory stages, either with or without aetiology-dependent treatment [4,7].
- 5. Uniformly-designed studies are lacking, to compare myocarditis among different patient subgroups, differing by variables like: clinical presentations, myocarditis stage, associated cardiac or extra-cardiac diseases, aetiology-based treatment, associated arrhythmic manifestations, diagnostic workup, and devices or ablation treatment [8,9,10].

AIMS

Our study has multiple aims (full detail in Table 1).

- 1. To compare EMB with nonivasive diagnostic techniques (CMR, DECT, PET scan, either alone or in association).
- 2. To assess the role of blood biomarkers for identification of aetiology, predisposition, prognosis, response to treatment, inflammatory activity, clinical presentation.
- 3. To describe myocarditis presenting with arrhythmias, with special focus on ventricular arrhythmias at different myocarditis stages and in different clinical contexts. To validate and generalize our model for optimal diagnostic and therapeutical management of arrhythmias in myocarditis patients (given the role of our hospital as an international referral center for arrhythmias ablation and management).

- 4. To evaluate the timing needed for myocarditis healing in different patients subgroups, as assessed by nonivasive imaging techniques (CMR, DECT, PET scan), either alone or in association.
- 5. To compare patients subgroups of myocarditis, in terms of epidemiology, aetiology, prognosis, and diagnostic-therapeutical strategies. Among the others, the main study subgroups will be:
 - A. Arrhythmic vs. non-arrhythmic myocarditis.
 - B. Arrhythmic myocarditis subgroups.
 - C. Non-arrhythmic myocarditis subrgoups (i.e.: fulminant, acute coronary syndrome-like, pericarditis-like, heart failure, nonischaemic dilated /hypokynetic cardiomyopathies of unknown aetiology...).
 - D. Infectious vs. aoutoimmune vs. toxic myocarditis.
 - E. Myocarditis treated by aetiology-based treatment vs. isolated cardiac medical treatment.
 - F. Myocarditis at different disease stages: acute, hyperacute, fulminant, chronic active, post-inflammatory, or active vs. previous vs. non-myocarditis.
 - G. Myocarditis presenting as organ-specific diseases vs. in the context of a genetic disorder or systemic disease.
 - H. Myocardits vs. peri-myocarditis/myo-pericarditis.
 - I. Other analyses.

STUDY DESIGN

Our study, previously designed as a single-center experience, is multicenter, observational and both retrospective and prospective.

Retrospective phase includes all clinical data occurring before the index event (hospitalization or clinically suspected myocarditis) and myocarditis diagnosis. Prospective phase includes all data following index event and myocarditis diagnosis.

Any adult patient with clinically suspected myocarditis, of any clinical presentation and any degree of severity, will be considered as suitable for study enrollment.

Patients will undergo diagnostic and therapeutical strategies considered as clinically indicated in a patient-tailored manner, as suggested by international guidelines recommendations and best local clinical practice. Patients will be free of either accepting or refusing any diagnostic or therapeutical proposal. Whenever accepted, data will be simply collected and analyzed.

Based on clinical presentation, patients will be divided into two groups, arrhthmic (group A) and non-arrhythmic (group NA, including any other clinical presentation).

Independently of A/NA groups, all patients will undergo optimal diagnostic and therapeutic strategies, as summarized in panel A. In parallel, special diagnostic and therapeutical strategies will be performed in patients with arrhythmic presentation or evidence of arrhythmias, as shown in panel B. Proposed flowcharts (panels A and B) represent only an approximate algorithm. Exceptions can be made in single cases, based on clinical indications.

Panel A – Diagnostic and therapeutical workup in all patients.

Independently of groups (A/NA), all patients will undergo optimal diagnostic and therapeutical workup, guided by updated scientific evidence merged with the clinical experience of the center.

Baseline diagnostic workup will include: complete blood exams, 12-leads ECG, continuous telemetric monitoring, transthoracic doppler echocardiogram, coronary artery imaging (coronary angiography or CT scan). Any other clinically relevant diagnostic test will be collected.

In life-threatening presentations (cardiogenic shock or malignant arrhythmias), support treatment by optimal medical therapy, inotropic or mechanical circulatory support, and acute-phase arrhythmia management (including cardioversion, defibrillation, or temporary pacing) will be performed, as indicated, before completing diagnostic workup. Final diagnosis of myocarditis will include, whenever applicable:

- A. For stable patients: 1) a second-level imaging technique (CMR as first choice; and/or DECT, PET, or multiple/fusion imaging techniques, based on clinical indications); followed by: 2) EMB, whenever clinically indicated. Blood exams for aetiology screening will be personalized upon clinical indications.
- B. For unstable patients: EMB only, as recommended. Blood exams for aetiology screening will be personalized upon clinical indications.

Diagnostic criteria for myocarditis, as assessed by any diagnostic technique, will be defined based on international scientific evidence and will be constantly updated. Similar considerations apply to myocarditis staging and aetiology definition. Whenever not available at local institutions, diagnostic exams can be performed and analyzed at external centers.

All patients with myocarditis (or any alternative final diagnosis), will undergo standard cardiological optimal medical treatment (COMT), as indicated. By converse, aetiology-dependent treatment will be performed only in patients with a final diagnosis of any *active* (acute, fulminant, chronic active) myocarditis of defined aetiology (EMB-proved). Multidisciplinary assessment, including infective disease specialists (in viral/infective myocarditis), immunologists (in non-infective/autoimmune myocarditis) or any other specialist as needed, will be used to identify indications to treatment, drug choice (either approved or with a justified off-lable indication), treatment duration and safety profile, aiming at the best patients' interest. Toxic myocarditis will be treated accordingly, by evaluating the opportunity of withdrawing pathogenic noxa.

This protocol will not interfere with local best clinical practice.

Patients with *non-active* myocarditis (previous or healed) or with non-myocarditis, will undergo "standard FU" (see below). Patients with *active* myocarditis will undergo "intensive FU" (see below).

Independently of FU modalities, diagnostic reassessment will be considered in the presence of at least one of the following *instability* criteria: a) new unexplained cardiac symptoms (dypnoea, chest pain, syncope, palpitation); b) new unexplained increase in troponin or natriuretic peptides; c) new imaging abnormal signs; d) new unexplained clinically relevant arrhythmias. Diagnostic reassessment will include second-level imaging and/or EMB, as shown above. Subsequent therapeutical workup will be in line with the above explanations. In stable patients or undergone myocarditis healing, exercise stress test will be obtained, whenever possible.

Panel B - Diagnostic and therapeutical workup of patients with arrhythmias

In parallel with (and independently of) Panel A content, patients with arrhythmias (group A) will undergo specific diagnostic and therapeutical management for arrhythmias, as a result of the integration between international guidelines recommendations and the experience of a third-level center international referral center (San Raffaele Hospital, Milan) for arrhythmia management and ablation.

To oversimplify, 4 groups of patients will be considered.

1. Group 1: major ventricular arrhythmias (haemodynamically unstable VT, hu-VT; ventricular fibrillation, VF).

After electrical stabilization and support treatment (panel A), indication to secondary prevention ICD implant will be multiparametric and patient-tailored. In patients with active myocarditis, subcutaneous ICD (S-ICD) or wearable CD (WCD) will be considered. Antiarrhythmic drugs will be considered in all Group 1 patients. In addition, all Group 1 patients will undergo COMT and aetiology-dependent treatment whenever applicable (panel A). Ablation of ventricular arrhythmias will be considered in patients with severe arrhythmic presentation, or symptomatic, or refractory to optimal medical treatment. Electrophysiological study (EPS) may be used in selected cases. A CRT-D will replace ICD whenever indicated.

2. Group 2: other ventricular arrhythmias (high-burden premature ventricular complexes = hb-PVC; nonsustained VT = NSVT; haemodynamically stable VT = hs-VT). Whenever clinically indicated, Group 2 patients will undergo invasive EPS (or in alternative nonivasive programmed ventricular stimulation in ICD carriers) to stratify arrhythmic risk. Patients with positive EPS will undergo ICD (or S-ICD/WCD) as in Group 1. Patients with negative EPS, as well as Group 2 cases not undergoing EPS, will undergo watchful waiting strategy (always with an intensive FU) with or without loop recorder implant: in these cases, ICD (or S-ICD/WCD) will be implanted only following documentation of relevant VA in FU. In addition, all Group 2 patients will undergo antiarrhythmic treatment, COMT and aetiology-dependent treatment whenever applicable (panel A). In symptomatic or drug-refractory cases, ablation of ventricular arrhythmias will be considered. A CRT-D will replace ICD whenever indicated.

3. Group 3: bradyarrhythmias (2nd type II or 3rd degree atrioventricular block = advanced AVB; critical sinus pauses = SND).

After electrical stabilization and support treatment (panel A), including the use of temporary pacemaker as a bridge-to-decision, patients will undergo watchful waiting strategy or definitive device implant. Instead of a pacemaker (PM), ICD will be considered in the presence of high-risk criteria for ventricular tachyarrhythmias, including: a) overlap with Group 1 presentation; b) overlap with Group 2 presentation, especially in the presence of positive EPS; c) other indications for primary prevention ICD implant (severe systolic dysfunction); d) signs of increased tachyarrhythmic risk (scar signs); e) patients with special aetiologies leading to an increased tachyarrhytmic risk (es: cardiac sarcoid, giant cell myocarditis, Chagas disease, overlapping genetic syndromes). In addition, all Group 3 patients will undergo COMT and aetiology-dependent treatment whenever applicable (panel A). A CRT-D or a CRT-P will replace ICD or PM, respectively, whenever indicated.

4. Group 4: supraventricular arrhythmias (atrial fibrillation = AF; atrial flutter = AFlu; atrial tachycardia = AT).

Following acute-phase rate control (RaC), stable rhythm control (RyC) strategy will be considered as the therapeutical target, together with appropriate anticoagulation, as needed. Normal sinus rhythm will be obtained through either electrical or pharmacological cardioversion. In patients with unsuccessful attempts of sinus rhythm conversion, optimal treatment of active myocarditis will be considered as a primary target. Following myocarditis healing, in the presence of persistent arrhythmias, patients will be considered for RyC via electrical or pharmacological cardioversion. Transcatheter ablation will be an option for patients with drug-symptomatic, recurrent or refractory arrhythmias. Permanent RaC strategy will be considered only in non responders. Widespread use of implantable loop recorders will apply, as clinically indicated. In addition, all Group 4 patients will undergo COMT and aetiology-dependent treatment whenever applicable (panel A).

STUDY POPULATION

We will enroll adult patients (age \geq 18 y), of any gender or ethnic group, evaulated for clinically suspected myocarditis. Patients can be enrolled from any medical environment or department, including inpatients, outpatients, and patients transferred from other hospitals. The same inclusion criteria will apply to the multicenter study (see below).

INCLUSION CRITERIA

- Written informed consent.
- Age \geq 18 years.

- Clinically suspected myocarditis [1].
- Enrollment performed by one of the participating Centers.

EXCLUSION CRITERIA

- Absence of written informed consent.
- Age < 18 years (paediatric population).

VARIABLES AND ENDPOINTS

The main study variables are reported in Table 1 and in CRF. Endpoints will include:

- Major endpoints: death; cardiac death; malignant ventricular arrhythmias (= VT, VF, appropriate ICD therapy); heart transplantation; end-stage heart failure.
- Minor endpoints: minor arrhythmias (NSVT; supraventricular arrhythmias; bradyarrhythmias); structural or functional myocardial abnormalities (any chamber dilation, systolic or diastolic dysfunction, including strain analysis, pericardial, vascular or valvular involvement, any other detectable abnormalities); abnormalities detectable by advanced imaging techniques (Lake Louise criteria and T-mapping techniques at CMR; any qualitative or quantitative imaging abnormality detectable by CMR, DECT or PET scan, or other imaging techniques, alone or in association); clinical variables (signs and symptoms related to cardiac or multisystemic disease; identification of associated diseases); blood exams abnormalities (inflammatory indexes; cardiac injury, inflammation or stress biomarkers; cardiac and extracardiac autoantibodies; genetic tests; tissue/organ damage indexes; markers of treatment toxicity; others); anatomical or functional abnormalities of coronary macro or microvascular structures (coronary angiography; CT scan; histology; provocative stress tests, nuclear medicine techniques); necessity of invasive elctrophysiological techniques (electrophysiological study; arrhythmia ablation; device implant) and related findings; indications and timing for primary and secondary prevention device implant, in relation with different therapeutic strategies; myocarditis recurrences; response to general and specific treatement; multiparametric modeling of prognostic risk stratification and response to treatment prediction; elaboration of multidisciplinary workup models.

The main pimary and secondary variables are reported in detail in Table 1.

Tabella 1

N	Aim	N patients	Primary Variables	Secondary variables

MYOCAR - Version V03 - Multicenter

Principal Investigators: [name] - [name]

1 Comparison between EMB 1000 Diagnostic Inflammation 	ory activity (presence; type;
and second level imaging concordance quantificat	
findings • Fibrosis (p	resence; type; quantification)

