	arrhythmias during FU)				• • •	Identification of optimal timing for any electrophysiological/arrhythmologic procedure Role of pharmacological antiarrhythmic treatment Role of aetiology-specific treatment on arrhythmic outcomes Identification of criteria for device implants (PM, ICD, S-ICD, CRT-D) in myocarditis patients Validation of therapeutic strategies and their optimal timing in patients with supraventricular arrhythmias, bradyarrhythmias, or ventricular arrhythmias Correlation between arrhytmia type/features with any other diagnostic exam performed at baseline or during FU (mainly EMB, CMR/DECT/PET, echocardiogram, stress tests,
					•	blood exams, genetic/blood/tissue/cell biomarkers) Indications and timing for device (ICD, CRT-D) implant in primary prevention, based on multiparametric risk assessment, and in relation to different general and aetiology- dependent treatments Other analyses
4	Evaluation of healing timing in myocarditis	500	•	Any degree of recovery by 3, 6, 9, 12 and > 12 months	• • • • •	Comparison of healing times in treated vs. untreated patients Correlations between healing times and clinical presentation types Correlations between healing times and any biomarker Correlations between healing times and any outcomes Validation of exercise stress test role after myocarditis healing Evaluation of PET scan or other diagnostic techniques as alternatives to CMR in special populations Other analyses
5	 Subrgoup analyses A. A vs. NA groups B. A myocarditis subgroups C. NA myocarditis subgroups (including fulminant) D. Infective vs. autoimmune vs. toxic forms E. Tretaed by aetiology- driven therapy vs. standard cardiological treatment 	500 (hugely variable in each subanalys is)	•	Differences in major outcomes	• • • • • •	Differences in minor outcomes Differences in any biomarker Differences in any diagnostic exam Differences in aetiology Differences in predisposition Differences in predisposition Differences in inflammatory activity Differences in pericardial involvement Differences in systemic involvement Differences in systemic involvement Differences in arrhythmias types and features Differences in clinical presentation Differences in treatment response, including novel treatments Validation of local aetiology/pathophysiology- dependent treatments (group E)

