- Intensive FU: cardiological (or multidiciplinary) assessment 1-2/y with blood exams (at least troponin, natriuretic peptides, and inflammatory indexes), 12-leads ECG, Holter

ECG monitoring, device interrogation (in device carriers), and color Doppler transthoracic echocardiogram. Minimal reassessment timespan is 2 weeks. At least one second-level imaging techniques (CMR, DECT, PET scan) will be performed by 12 months (approximately at 3, 6, 9, or 12 months based on clinical indications). Exercise stress test will be performed whenever clinically indicated, usually not before proved myocarditis healing. Other exams will be performed based on clinical indications.

STUDY DURATION

Estimated study duration is 23 years (from Jaunary 2013 to December 2035). In detail:

- Retrospective enrollment: from January 2013 to local institute review board approval.
- Prospective enrollment: from local institute review board approval to Dicember 2025 (estimated enrollment end).
- FU duration per patient: 10 years.
- Estimated last FU for last enrolled patient: December 2035.

CONFOUNDING FACTORS

Not applicable.

EPIDEMIOLOGIC DATA

Because of multiple clinical presentations and heterogeneous diagnostic techniques, myocarditis incidence is widely variable [1].

At our institution, the mean rate of clinically suspected myocarditis is not inferior to 4 new cases/month. Epidemiology may be different at other centers.

Target numbers reported in Table 1 are reasonable.

DATA COLLECTION AND STATISTICAL ANALYSIS

Two enrollment modalities are accepted for this study: 1) prospective enrollment: at myocarditis diagnosis (following local institute review board approval); 2) retrospective enrollment: during FU of myocarditis patients (diagnosed before local institute review board approval).

Considering incidence rate, local and general epidemiology, enrollment of 1000 myocarditis cases by December 20205 is expected, including retrospective and prospective enrollment. For aim 1, 95% confidence intervals of 81-89% and of 75-85% are estimated for EMB and CMR, with 85% and 80% sensitivity, respectively. These data are consistent with updated knowledge. EMB will be considered as the diagnostic gold standard, as indicated [1].

Both baseline and FU data will be collected for each enrolled patient. CRF form reports the main study variables, in the form of an Excel document.

Statistical analyses will be performed by certified programs (i.e. SPSS).

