Data will be presented as mean/median and standard deviation/interquartile range, or as contingency tables, depending on variables type and distribution. Parametric and non-parametric tests will be used accordingly. Confidence intervals will be set at 95%. Statistical significance threshold will be set at p < 0.05. Regression models will be used for univariable and multivariable risk stratification and survival analyses.

Either in all patients or in subgroups, appropriate statistical tests will be used for general and specific analyses, as needed to address each study aim (Table 1).

ETHICAL ISSUES

Our study will be performed in accordance with Helsinki Declaration and current laws regarding observational prospective and retrospective studies.

Diagnostic and therapeutical workup will not differ from daily clinical practice a tour hospital, as the result of updated international scientific evidence, integrated by the experience of a referral center for myocarditis and arrhythmias management, aiming at the best patients' interest. Follow-up timeline and diagnostic exams will be required as clinically needed. No randomization procedures will be performed. Patient grouping will be "spontaneous", based on clinical features and personalized overall workup. This study will respect the autonomy principle for any patient. At any time, patients will be free to accept or refuse any diagnostic or therapeutical proposal. As in daily clinical practice, critical or exceptional diagnostic and therapeutical options will be discussed in a multisiciplinary team and shared with patients, as needed. Per protocol, data will be simply collected and analyzed, without interfering with the best clinical practice. Thus, for any diagnostic exam or treatment, no special adverse reactions are expected, as compared to what observed in daily clinical practice.

Written informed consent will be obtained for any enrolled patient. No physical or psychosocial risks are expected regarding study procedures, informed consent, or authorization to use personal data.

Institutional review board evaluation is necessary to approve the present study protocol.

All data will be made anonymous. Analyses results will be published in international medical journals with impact factors.

REFERENCES

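### Confounding is declared not applicable and no centre or referral term is named, so the arrhythmic versus non-arrhythmic comparison of major outcomes may be confounded by centre

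*Protocol*

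**What the plan says.** **Design.** Under Study Design: "Our study, previously designed as a single-center experience, is multicenter, observational and both retrospective and prospective". Allocation to groups follows presentation: "Based on clinical presentation, patients will be divided into two groups", arrhythmic (A) and non-arrhythmic (NA). Diagnosis and treatment follow guidelines together with local practice.

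**Head centre.** Rationale, item 3, describes it in these words: "At our hospital, which is an international referral center for ventricular arrhythmias management and ablation". The same sentence reports that myocarditis proved to be the cause in an appreciable part of its otherwise unexplained arrhythmia cases. No count or share is given. Study Population admits patients transferred from other hospitals, alongside inpatients and outpatients.

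**The comparison.** The first subgroup contrast under aim 5 is "Arrhythmic vs. non-arrhythmic myocarditis" (called 5A below). Table 1 gives the primary variable for aim 5 as "Differences in major outcomes" and a target of 500 patients, with a note that the number varies greatly between sub-analyses. Major endpoints include VT, VF and appropriate ICD therapy.

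**Confounding and analysis.** The section headed Confounding Factors holds nothing but a declaration that the item is not applicable. Epidemiologic Data, after giving the head centre's case rate, adds: "Epidemiology may be different at other centers". Data Collection and Statistical Analysis says: "Either in all patients or in subgroups, appropriate statistical tests will be used for general and specific analyses", as each aim requires. It also plans univariable and multivariable regression for risk stratification and survival, without naming covariates. Centre is not mentioned there as a factor, stratum or covariate.

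**The concern.** A factor confounds 5A if it is related both to being in group A and to the outcome. The protocol's own text makes centre a candidate on both counts.

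- **Link to group.** A referral centre for ventricular arrhythmias that accepts transfers may well enrol a higher proportion of arrhythmic cases than other participating hospitals.
- **Link to outcome.** Referred patients may be sicker, and care follows local practice. Several major endpoints are arrhythmic events or device therapies, whose detection depends on how often a centre implants devices and monitors rhythm.

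If both links hold, a difference between centres would be reported as a prognostic effect of arrhythmic presentation. Aim 3 also intends to validate and generalise the head centre's management model, so whether findings hold outside that centre is a question the study itself raises.

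An analysis plan can properly settle the covariate list later. The difficulty here is that the protocol makes a positive statement that confounding does not apply. That statement is wrong for a non-randomised comparison, and a later plan that adjusted for centre would contradict it.

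**Working it through.** The protocol states no effect size, power or event rate for 5A, and no A/NA split by centre, so it has no figure of its own to reproduce on this point. Its one precision statement concerns sensitivity in aim 1 and has no bearing here. What follows shows how large the bias could be under stated assumptions.

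**Inputs from the protocol**
- 500 patients for aim 5 (Table 1). An equal split, 250 per group, is assumed.
- Significance threshold 0.05. Sidedness is not stated; two-sided is assumed.
- At least 4 suspected cases a month at the head centre (Epidemiologic Data).

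**Inputs assumed**
- No A versus NA difference within any centre.
- Shares from the head centre, and major-event risks, as listed below.

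**Formulas**
- Crude risk in a group = (share from head centre × head-centre risk) + (share from elsewhere × risk elsewhere).
- z = difference / √[p₁(1 − p₁)/n + p₂(1 − p₂)/n], with n = 250.
- Probability of p < 0.05 = Φ(z − 1.96) + Φ(−z − 1.96).

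**Case 1: 70% of A and 30% of NA from the head centre; risk 30% there, 15% elsewhere**
- A: 0.7 × 0.30 + 0.3 × 0.15 = 0.255. NA: 0.3 × 0.30 + 0.7 × 0.15 = 0.195.
- Risk ratio 0.255/0.195 = 1.31. This does not depend on sample size.
- z = 0.06/√(0.255 × 0.745/250 + 0.195 × 0.805/250) = 0.06/0.0373 = 1.61. Rejection probability about 36%.

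**Case 2: shares 60% and 40%; risks as in case 1**
- A: 0.24. NA: 0.21. Risk ratio 1.14. z = 0.03/0.0373 = 0.80. Rejection about 13%.

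**Case 3: shares 70% and 30%; risk 25% against 15%**
- A: 0.22. NA: 0.18. Risk ratio 1.22. z = 0.04/0.0357 = 1.12. Rejection about 20%.

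**A second set, using the protocol's accrual rate.** Cases 1 to 3 imply that half of all patients come from the head centre. At 4 a month over 156 months (January 2013 to December 2025), the head centre would contribute 624 of 1000, or 62.4%. This is approximate: the rate is a minimum, counts suspected cases, and is taken as constant with every case enrolled. With N = 500, that share, and a two-proportion test with pooled variance under the null:

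| A share, head / elsewhere | Event risk, head / elsewhere | Crude odds ratio | Rejection |
|---|---|---|---|
| 40% / 40% | 20% / 10% | 1.00 | 5% |
| 60% / 40% | 15% / 10% | 1.09 | 6% |
| 60% / 20% | 20% / 10% | 1.32 | 21% |
| 70% / 20% | 20% / 10% | 1.42 | 30% |

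The third row in full: A risk = (0.624 × 0.6 × 0.20 + 0.376 × 0.2 × 0.10)/(0.624 × 0.6 + 0.376 × 0.2) = 0.0824/0.4496 = 18.3%. NA risk = (0.624 × 0.4 × 0.20 + 0.376 × 0.8 × 0.10)/0.5504 = 0.0800/0.5504 = 14.5%.

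In every scenario the within-centre effect is zero by construction, so an analysis stratified by centre has an odds ratio of 1.00 and a nominal 5% rejection rate.

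**The case against.** The strongest reply is that the protocol never says centres will be pooled without regard to centre. The sentence on tests in all patients or subgroups is generic, multivariable models are planned, and naming their covariates is ordinary analysis-plan content. That stands. A reader might infer that an unadjusted pooled analysis has been decided; the text does not support this. What remains is the confounding entry itself, which is a statement and not a silence.

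A reader might also infer that arrhythmic cases do concentrate at the head centre. This is plausible but undocumented: there are no A/NA counts by centre and the other centres are not described. The remark about differing epidemiology sits beside an incidence rate and does not plainly concede a different case mix. Nor does the protocol say that transfers are selected for severity or go only to the head centre.

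Three limits on scope and size also stand.
- Reading the 1000 planned cases as 500 per group would raise the rejection rates in cases 1 to 3 to 62%, 21% and 35%, but Table 1 assigns 500 patients to aim 5.
- The argument covers 5A only. Subgroup contrasts 5B and 5C lie wholly within A and wholly within NA, and neither is shown to be affected.
- The calculation gives all head-centre patients, A and NA alike, the higher risk. If only transferred arrhythmic patients are more severe, A and NA differ within the head centre too, and stratifying by centre will not remove that.

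**Conclusion.** The point holds as a risk of confounding that the protocol denies, not as a demonstrated bias. Declaring confounding inapplicable is wrong for a non-randomised multicentre comparison of outcomes, and the protocol's own description of its head centre, its transfers and its reliance on local practice shows why centre and referral should be considered.

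Under the assumptions in cases 1 to 3, the crude risk ratio runs from 1.14 to 1.31 and the false-positive rate from about 13% to 36% at 250 per group. With the accrual-based head-centre share, the tabulated scenarios run from no inflation (5%) to 30%. All shares and risks are assumed. The bias is zero if either the arrhythmic share or the outcome risk and its ascertainment are the same across centres. The protocol should be changed, but nothing in it shows that the actual bias will be large.

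**What to change.** 1. Replace the entry under Confounding Factors with a statement that enrolling centre is a potential confounder of the A versus NA comparison, together with referral status.
2. State that the 5A tests and the regression and survival models are stratified by or adjusted for centre, with small centres combined.
3. Add route of entry (direct or transferred) to those models where it is recorded.
4. Report A versus NA separately for the head centre and for the other centres as a sensitivity analysis.
5. State the remaining limit: centre adjustment does not remove selection for severity among arrhythmic patients transferred to the head centre.

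**Cost.** Enrolling centre is known for every patient, because enrolment by a participating centre is an inclusion criterion. Precision falls slightly where centres are small. Route of entry may be incomplete for patients enrolled retrospectively, back to 2013; the protocol does not show that it is collected.
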